## 1.2 Bone Marrow Mononuclear Cells (BMMNC) for N-IHF

To date, limited number of randomized controlled trials has investigated intracoronary or intracardiac infusion of BMMNCs in patients with N-IHF. The First-in-Man ABCD (Autologous Bone Marrow Cells in Dilated Cardiomyopathy) Trial was a prospective, randomized, open, and parallel 2-arm study in a stable HF population with a history of dilated cardiomyopathy. In this study autologous bone marrow–derived stem cells were used which were administered intracoronary. This study showed a significant improvement in the left ventricular ejection fraction (LVEF) and New York Heart Association (NYHA) Functional Classification. The Transplantation of Progenitor Cells and Functional Regeneration Enhancement Pilot Trial in Patients with Nonischemic Dilated Cardiomyopathy (TOPCARE-DCM) was a prospective, open-label study testing the efficacy of selective intracoronary infusion of BMMNC on LV function. This study showed that intracoronary administration of bone marrow–derived progenitor cells seems to be associated with improvements in cardiac contractile and microvascular function. The results of the first randomized, double blind, placebo-controlled trial worldwide investigating the role of G-CSF and BMMNC for cardiac function improvement are expected.

## 2 MESENCHYMAL STEM CELLS

Mesenchymal stem cells (MSCs), also known as marrow stromal cells, represent 0.001%–0.01% of all nucleated bone marrow cells. They are self-renewing, multipotent progenitor cells with the capacity to differentiate into several distinct mesenchymal lineages including osteoblasts, chondrocytes, adipocytes, endothelial cells, vascular smooth muscle cells, and cardiomyocytes. Although MSCs were initially identified in the bone marrow, they have been isolated from a number of tissues including muscle, adipose and connective tissues. Human MSCs have been defined as cells that (1) are plastic-adherent, (2) express CD105, CD73 and CD90, and lack expression of CD45CD34, CD14 or CD11b, CD79a or CD19 and HLA-DR surface molecules, and (3) differentiate to osteoblasts, adipocytes and chondroblasts *in vitro*. Even after expansion *in vitro*, mesenchymal differentiation potential of MSCs is retained.

## 2.1 Mechanisms of Action of MSCs

Although there is *in vitro* and preclinical evidence that MSCs differentiate into cardiomyocyte-like cells with sarcomeric organization when injected into the adult myocardium, it appears that a low percentage of cells **Protocol:** STEM-104-M-CHF 12 19FEB2014

engraft, independently of cell source, dose, and route of delivery. In ischemic settings and on appropriate growth factor and/or cytokine stimulation, MSCs readily acquire an endothelial cell phenotype *in vitro*, form capillary-like networks in extracellular matrix gels, express and secrete proangiogenic growth factors, and increase blood vessel growth *in vivo*. MSCs also participate in the formation of the vessel media by differentiating into smooth muscle cells and fibroblasts, and the vascular tree is a predominant reservoir for tissue-specific MSCs that express CD146, NG2, and PDGFRB (platelet-derived growth factor receptor,  $\beta$  polypeptide) but no hematopoietic, endothelial, or myogenic markers. MSCs delay scar formation due to connective tissue remodeling indicating that they may directly interact with extracellular matrix components.

MSCs secrete a wide spectrum of growth and other paracrine factors including vascular endothelial growth factor (VEGF), HGF, insulin-like growth factor (IGF)-1, TGF- $\beta$ , basic fibroblast growth factor (bFGF), leukemia inhibitory factor (LIF), stromal-derived factor (SDF)-1, angiopoietin, interleukins, numerous chemoattractants, and "survival factors" that exert antiapoptotic effects. Their secretion profile is importantly influenced by the inflammatory milieu, hypoxia, and mechanical stress. These paracrine actions may be sufficient to enhance repair and regeneration even in remote tissues. Evidence suggests that secreted phospholipid particles (exosomes) rather than or in addition to cytokine proteins mediate MSC cardioprotection. In the *in vivo* setting, reduced numbers of apoptotic cells are found in the vicinity of transplanted MSCs that may explain the reduction in infarct size despite absence of formation of new cardiomyocytes.

MSCs also reduce myocardial fibrosis and thereby attenuate LV dilatation by modulating the expression of extracellular matrix proteins and matrix metalloproteinases. They secrete antiapoptotic and antifibrotic factors including hepatocyte growth factor and adrenomedullin. Indeed, MSC-conditioned medium decreases type I and III collagen expression, attenuates proliferation of fibroblasts, and upregulates expression of elastin, resulting in reduction of myocardial fibrosis and favorable changes in remodeling. MSCs increased proliferation of endogenous CSCs, enhanced lineage commitment of the CSCs, and reconstitution of niche-like structures. Importantly, cardiac MRI documented a reduction of infarct size as early as 4 days after cell injection, which was progressive over 8 weeks.

## 2.2 Preclinical Experience with MSCs for Heart Disease

MSC transplantation using either autologous or allogeneic cells in animal models leads to reduction of ischemia, reduced apoptosis, and increased angio- and arteriogenesis in ischemic tissue, leading to improved tissue vascularization and function. Successful delivery strategies include intravenous, intramyocardial, and intracoronary administration not only in ischemic but models of non-ischemic cardiomyopathy.

Intravenous injection of 3 and 10 million allogeneic porcine MSCs/kg at the onset of reperfusion in a closedchest pig model of acute MI increased vascular density, hyperemic infarct region blood flow, and LV contractile function evaluated by pressure–volume indices after 12 weeks compared to the controls. The functional and vascular density data suggest that the 1 million MSCs/kg dose may represent the lowest effective dose for protection. In another study, apical infarction in swine was created and bone marrow derived MSCs injected intravenously 30 min post-reperfusion. At 3 months, treated animals had higher LVEF and less wall thickening of non-infarcted myocardium compared to controls. Similarly, Kocher et al. reported an increase in microvascularity in the rat infarct model with intravenous injection of human endothelial progenitors. In a porcine model of occlusion-reperfusion, LV function measured by MRI 8 weeks after MI was better in hearts receiving MSCs by intramyocardial injection 3 days after infarction. Others reported improved LV function in the absence of observable MSCs one month after transplantation.

In contrast to administration of stem cells by direct myocardial injection or intracoronary administration, intravenous delivery results in entrapment of cells mainly in the lungs during initial distribution reducing recruitment to the site of infarction. Intravenous infusion resulted in a lower efficiency of cell uptake compared to direct intramyocardial injection. However, a recent comparative study with intracoronary or intravenous injection of BMMNCs found accumulation of cells in the infarcted myocardium although more cells accumulate after intracoronary than after intravenous injection. It is therefore likely that paracrine release by MSCs of growth factors and cytokines is largely responsible for their therapeutic effect after intravenous administration. **Protocol:** STEM-104-M-CHF 13 19FEB2014

## 2.3 Allogeneic versus Autologous MSCs

Bone marrow-derived MSCs are to some extent immunoprivileged, and allogeneic MSCs may escape elimination by the host immune system because they do not express MHC class II receptors and only low levels of MHC class I receptors. As with endothelial progenitor cells, MSCs are subject to age- and disease-related changes, decreasing in number in the bone marrow with age. Although terminal differentiation is preserved in older MSCs, it is lower when compared to younger cells. The gene expression profile of aging MSCs shows increased abundance of differentiation- and growth arrest-related transcripts and downregulation of transcripts involved in RNA processing. Moreover, these MSCs did not improve cardiac function. These findings support the concept that allogeneic MSCs from young donors may have greater regenerative capacity than autologous cells from older subjects with CAD.

## 2.4 Modifying MSCs for Cardiac Regeneration

Overexpression of antiapoptotic proteins and growth factors, and inhibition of MSC differentiation by blocking Wnt and BMP signaling pathways, have proven powerful strategies to enhance the cardiac regeneration capacity of MSCs, but their clinical application remains problematic at present. Experimentally, several modifications in MSCs have resulted in their enhanced functionality. Among these strategies are MSCs enriched for Stro-1 expression, treatment with heat shock proteins, preconditioning by oxidative stress, diazoxide-mediated NF-κB activation, and nitric oxide donors, hyperbaric oxygenation of the recipient heart, adjunct pharmacologic therapy with statins and estradiol, sildenafil, and oxytocin. Mechanical prestimulation by microbubbles and embedding MSCs in extracellular matrix components or artificial polymer scaffolds may facilitate cell retention. One strategy that is ready for clinical translation is use of enhanced MSCs grown in hypoxic culture conditions.

## 2.5 Potentiation of MSCs with Hypoxic Culture

It is well known that stem cells reside in defined microenvironmental niches and that oxygen conditions critically regulate cellular responses. For example, oxygen tension in human bone marrow is ~3.0%. Hypoxic culture conditions can maintain MSCs in an undifferentiated state that favors stem cell self-renewal. It enhances expression of genes involved in developing mesodermal and non-mesodermal cell lines, increases multipotency and transdifferentiation, increases the half- life of VEGF mRNA significantly (6-8h in low oxygen conditions compared to 30-40 min. in normoxia), and decreases transversions from oxidative damage.

## 2.6 Potency of MSCs Cultured in a Hypoxic Environment

Stemedica has obtained a patent for culture of human donor MSCs in hypoxic conditions (ischemia-tolerant MSCs, itMSCs). The biological potency of these cells has been studied in vitro experiments compared to MSCs cultured in normoxic conditions. itMSCs formed more colonies in culture assays, had a greater proliferation rate, produced greater quantities of VEGF, SDF-1, HIF-1alpha, and angiopoeitin 1. itMSCs also demonstrated greater migratory capacity in response to chemokines and cytokines, and formed more gap junctions than normoxic MSCs. In summary, itMSCs compared to those grown in normoxic conditions have (1) a higher proliferation rate, (2) higher clonogenicity as determined by colony forming unit assay, (3) increased production of cytokines participating in homing of host stem cells to the site of injury (SDF-1) and in neovascularization (VEGF), (4) higher resistance to factors adversely affecting performance of MSC at the site of injury such as tumor necrosis factor, (5) higher expression of connexins, proteins involved in cell communication via gap junctions, (6) accelerated and enhanced differentiation into certain types of tissues such as cartilage, and (7) increased migration towards the factors produced at the ischemic site such as Hepatocyte Growth Factor. These properties of itMSCs likely increase their ability to migrate to ischemic tissues, enhance angiogenesis and arteriogenesis through paracrine effects, inhibit apoptosis, and mobilize host progenitors to promote tissue regeneration.

In vivo bio-distribution studies after intravenous injection in a rat model of ischemic stroke demonstrate a greater retention of human itMSC cells in stroke animals as compared to controls. With radiolabelled cells, it was clear that most of the itMSCs reside in lungs after 1 hour of intravenous injection, but a greater number are present in stroke animals compared to controls. After 24 hrs, the majority of itMSCs were found in the kidneys and liver, but were also greater in stroke animals compared to controls. After 72 hours, very little **Protocol:** STEM-104-M-CHF 14 19FEB2014

activity was detected in control animals, while there was significant activity detected in the liver and spleen of stroke animals. Very little activity in either group was noted after 5 days.

## 2.7 Clinical Experience with Stemedica itMSCs

Two clinical studies are currently ongoing using cells prepared at Stemedica's cGMP manufacturing facility. The first study targets ischemic stroke and is being conducted at the University of California, San Diego (UCSD), and at Mercy Gilbert Medical Center in Gilbert, Arizona using Stemedica's specially formulated ischemic adult allogeneic mesenchymal stem cells under US IND 14328. Stemedica completed the Phase I enrollment and treatment of 15 patients. All safety data were provided to DSMB for review. Only one mild event was possibly related to the study product. There were no clinically significant abnormalities reported on any post-administration scans or on post-administration physical examinations. In the second study "Intravenous Administration of Ischemic Tolerant Allogeneic Mesenchymal Stem Cells for Acute Coronary Syndrome Patients," Stemedica Cell Technologies, Inc. provided cGMP allogeneic itMSCs to the National Scientific Medical Center (NSMC) in Astana, Kazakhstan to conduct a clinical study in patients with STEMI, Principal Investigators: Professors [name], MD, PhD and [name], PhD . itMSCs were provided under 21 CFR §312.110 (4)(b) regulations and the study was conducted in compliance with the ICH-E6 (Good Clinical Practice) guidelines and all subjects provided signed informed consent. Nineteen subjects in the itMSC group received intravenously. There were no deaths and no SAEs reported to be related to the study drug. In 19 itMSC treated and 15 open control patients, i.v. injection of 45-50 million cells 7 days after stenting for STEMI was administered without any SAEs reported. LVEF improved significantly from 42.1% to 52.3% and 54.7% after 3 and 6 months, respectively. In contrast there was no improvement in LVEF in the control group; LVEF 42.3%, 42.8% and 46.1%, at baseline, 3 and 6 months respectively. Similar changes in end-systolic and end-diastolic volumes were noted. There was also an increase reported in circulating levels of growth factors (VEGF and FGF) in the itMSC treated group, and CRP and BNP levels were lower in the treated group compared to controls during follow-up.

# 2.8 Clinical Trials with MSCs in Heart Disease

A few studies using either allogeneic or autologous MSCs employing different delivery strategies have been performed in subjects with a variety of cardiac diseases including HF, STEMI, and chronic ischemia.

# 2.8.1 STEMI Trials with MSCs

In 3 studies where autologous bone marrow-derived MSCs were injected i.c. into the infarct artery of patients with STEMI, there were no serious adverse events reported, and regional and global LV function improved. Intracoronary infusion of bone-marrow-derived MSCs in 69 patients with STEMI showed improvement in perfusion defects at 3 months after the therapy with improvement of LVEF and LV chamber size. In 11 patients with STEMI treated with a combination of autologous bone marrow MSCs and endothelial progenitor cells, LV function and perfusion were better in MSC-treated patients and there was a reduction in malignant arrhythmia that indicated a reduced arrhythmogenic potential.

An allogeneic MSC product (Prochymal by Osiris Therapeutics, Columbia, MD) was administered intravenously in 53 patients with STEMI using a double-blind, placebo-controlled, dose-ranging (0.5, 1.6, and 5 million cells/kg) design. This demonstrated that intravenous infusion of hMSCs was safe, ventricular tachycardia episodes were lowered, and pulmonary function improved (forced expiratory volume) compared to placebo. Global symptom score in all patients and LVEF in the subset of anterior MI patients were both significantly better in hMSCs versus placebo subjects. In the cardiac MRI substudy, hMSC treatment increased LVEF and led to reverse remodeling.

# 2.8.2 MSC Trials in Heart Failure and Chronic Ischemia

In a randomized trial in patients with severe chronic ischemic cardiomyopathy, MSC-treated patients had significantly improved LVEF, exercise capacity, and change of New York Heart Association (NYHA) class. The POSEIDON trial studied patients with ischemic cardiomyopathy and compared autologous and allogeneic MSCs administered transendocardially via injection catheters. Thirty patients were randomly assigned to 1of 6 permutations of cell origin (self or donor) and dosage (n=5 patients each), and the safety and efficacy of self-**Protocol:** STEM-104-M-CHF 15 19FEB2014

derived MSCs with allogeneic MSCs was studied. Twenty million, 100 million, or 200 million cells were delivered by transendocardial injection into 10 LV sites. Relative to baseline, autologous but not allogeneic MSC therapy was associated with an improvement in the 6-minute walk test and the MLHFQ score, but neither improved exercise VO2 max. Low-dose concentration MSCs (20 million cells) produced greatest reductions in LV volumes and increased EF. Allogeneic MSCs did not stimulate significant donor-specific alloimmune reactions.

#### 2.9 **Rationale for Study Design**

Allogeneic MSCs are excellent for consideration for cell therapy in patients with IHF for the following reasons:

- (a) Human MSCs are accessible and their isolation and expansion to clinical scale in a relatively short period of time is feasible
- (b) Patients are spared the discomfort of harvesting procedures
- (c) Early therapy is feasible without the delay imposed by autologous cell cultures
- (d) MSCs can be biopreserved with minimal loss of potency and stored for point-of-care delivery
- (e) Human trials of MSCs thus far have shown no adverse reactions to allogeneic versus autologous MSC transplants, enabling creation of an inventory of third-party donor MSCs to widen the number of patients treated by a single isolation
- (f) MSC transplantation is considered safe and has been tested in Phase I clinical trials of cardiovascular, neurological, and immunological disease with encouraging results
- (q) Preliminary Phase I studies with Stemedica itMSCs administered in patients with ischemic stroke and STEMI has proven to be safe and associated with some improvement in clinical outcomes.

#### 3 **OBJECTIVES**

#### 3.1 **Primary Objective**

To assess the safety of human allogeneic mesenchymal bone marrow cells (aMBMC) administered intravenously to subjects with N-IHF.

#### 3.2 Secondary Objective

To assess the effects of intravenously delivered human aMBMC on (a) left ventricular (LV) structure and function, and (b) clinical status of subjects with N-IHF.

#### 4 STUDY DESIGN

#### 4.1 Description of the Study

This is a Phase IIa, single-blind, placebo-controlled, crossover, multi-center, randomized study in subjects with N-IHF. Within 3 ±2 days all study participants who meet the eligibility criteria will receive the treatment.

The study will enroll a minimum of 20 subjects and will consist of 2 cohorts. Enrolled subjects will be randomized at 1:1 into an experimental group (n=10), or a placebo group (n=10). Subjects in the experimental group will receive 1.5 million cells per kg and subjects in the placebo group will receive 1 mL/kg LRS. At 90 days the two groups will change arms and the placebo group will receive 1.5 million cells per kg and the initially treated group will receive a Lactated Ringer's Solution (LRS) at a volume of 1 mL/kg.

After discharge, subjects will have safety evaluations per Appendix A. Adverse events, concomitant medications, and assessments will be recorded at each follow-up visit. Complete examinations will be used to assess disability and functional status at baseline (prior to treatment), and at the visits scheduled at 30, 60, and 90, after the initial administration. The same process will be followed at visits scheduled at 30, 60, and 90 days after the new administration (crossover phase). A baseline magnetic resonance imaging (MRI) with delayed contrast enhancement and T2 imaging, as well as a full 2D and Doppler transthoracic echocardiography with speckle-tracking will be performed at baseline and at specific time points during follow-up. All performed MRIs will be assessed in a blinded core lab.

Subjects will continue all of their regular medications unless contraindicated. Subjects may be administered beta-blockers, ACE inhibitors or angiotensin receptors blockers, mineralocorticoid receptor antagonists, statin agents, or other medications, as tolerated. Protocol: STEM-104-M-CHF 16 19FEB2014

# 4.2 Endpoints

## PRIMARY ENDPOINT

## Safety

Baseline and days 30, 60, and 90 post-initial infusion. After the crossover phase all patients will be evaluated at days 30, 60, and 90 days post the new infusion

- 8. Procedural complications
- 9. Vital signs
  - a. Temperature
  - b. Systolic blood pressure/diastolic blood pressure
  - c. Heart rate
  - d. Respiratory rate
  - e. Weight
- 10. Changes in heart failure medications
- 11. Clinical arrhythmias, defibrillator firing and anti-tachycardia pacing
- 12. Laboratory tests
  - a. CBC/PLT/differential
  - b. Chemistry-12, including liver function tests
  - c. Creatinine kinase
  - d. Troponin-I
- 13. Electrocardiogram
- 14. Composite of all-cause mortality all-cause admission and need for co-intervention. E.g. IV diuretics for worsening heart failure (RADIENCE trial criteria).

## Baseline and day-90 post infusion

Pulmonary function test

## SECONDARY ENDPOINT

## Efficacy

Change in LVEF from baseline to day 90 post-initial infusion. After the crossover phase all patients will be evaluated for change from the new baseline (day 90 after the initial phase) to day 90 post new infusion

## EXPLORATORY ENDPOINTS

Changes between baseline and days 90 post-initial infusion. After the crossover phase all patients will be evaluated for changes from the new baseline (day 90 after the initial phase) to day 90 post new infusion. MRI

- 5. Left ventricular end systolic volume index
- 6. Wall motion segmental score
- 7. LV end-systolic and end-diastolic dimensions
- 8. T2 MRI imaging

Changes between baseline and days 90 post-initial infusion. After the crossover phase all patients will be evaluated for changes from the new baseline (day 90 after the initial phase) to day 90 post new infusion. Echocardiogram

- 4. Changes in LV mechanics by speckle-tracking echocardiography (longitudinal and circumferential strain and strain rate)
- 5. Estimated systolic pulmonary artery pressures
- 6. Changes in MR severity (most patients have mild to moderate MR).

Changes between baseline and days 30, 60, and 90 post-initial infusion. After the crossover phase all patients will be evaluated for changes from the new baseline (day 90 after the initial phase) to day 30 and 90 post new infusion.

Exercise capacity

6 minute walk distance

Health status

- a. New York Heart Association Class (NYHA) class
- b. Kansas City Cardiomyopathy Questionnaire

Heart failure status

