## STATISTICAL METHODS

All randomized subjects who receive at least part of a dose of aMBMC or LRS will be included in the safety analysis. Subject safety data will be analyzed by actual dose level (i.e., number of cells/kg). Adverse events will be coded according to the MedDRA adverse event dictionary. The results will be tabulated to examine their frequency, affected organ systems, severity and relationship to study stem cell administration. The results of laboratory tests will be similarly evaluated. The efficacy analyses will include subjects that received the full dose of aMBMC or LRS and have the appropriate follow-up completed at the scheduled assessments (i.e., efficacy evaluable population). Safety measures include the composite of all-cause mortality, admission for worsening HF and all-cause admissions. Measurement of left ventricle end diastolic volume, left ventricle end systolic volume, left ventricular ejection fraction (LVEF), longitudinal strain and strain rate, global and segmental strain and strain rate, exercise capacity by 6 minute walk distance test, biomarkers, Kansas City Cardiomyopathy Questionnaire (KCCQ) and the New York Heart Association (NYHA) Classification will be completed in the entire efficacy evaluable population. A formal statistical analysis plan will be conducted in accordance with the guidelines of Good Clinical Practice (GCP), including the archiving of essential documents.

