## Echocardiography

- A full 2D and Doppler echocardiogram will be performed at screening, at day 90, after initial infusion. After • the crossover phase a full 2D and Doppler echocardiogram will be performed at day 90 after the new infusion.
- Images will be acquired with the patient positioned in the recumbent lateral position. Left ventricular • volumes will be determined at end-diastole and end-systole by quantitative biplane assessment. Endocardial borders will be manually traced from apical four-chamber and two-chamber views. Left ventricular volumes will be used to calculate ejection fraction using the biplane modified Simpson's summation-of-disks method recommended by the American Society of Echocardiography.
- High frame-rate images of the LV in the three apical views (4-chamber, 2-chamber, and apical long axis) • will be acquired for speckle tracking echocardiography. Images will be analyzed offline on a dedicated workstation using EchoPAC BTO 12 (GE Healthcare) software for calculation of segmental and global 19FEB2014

longitudinal strain and strain rate. Global longitudinal strain and strain rate will be calculated from all 18 segments of the LV. Segmental strain and strain rate will be calculated for each segment separately. To assess effect of therapy on impaired regions, we will average strain and strain rate of the dysfunctional segments at baseline and compare the average of these segments over time.

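### Circumferential strain and strain rate are listed as exploratory echo endpoints, but section 7.1 specifies no image acquisition or calculation for them

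*Combined protocol and SAP*

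**What the plan says.** The synopsis and section 4.2 give the same echocardiographic exploratory endpoint: "Changes in LV mechanics by speckle-tracking echocardiography (longitudinal and circumferential strain and strain rate". It is assessed as change from baseline to day 90 after the initial infusion, and again from the new baseline to day 90 after the crossover infusion.

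Section 7.1, Echocardiography, is the only place that describes how the images are obtained and read:

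- Views for speckle tracking: "High frame-rate images of the LV in the three apical views (4-chamber, 2-chamber, and apical long axis"; these "will be acquired for speckle tracking echocardiography".
- Global output: "Global longitudinal strain and strain rate will be calculated from all 18 segments of the LV".
- Segmental output: "Segmental strain and strain rate will be calculated for each segment separately". The sentence before it describes the offline segmental and global analysis as longitudinal.
- Views for volumes and ejection fraction: "Endocardial borders will be manually traced from apical four-chamber and two-chamber views".

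The synopsis, under Statistical Methods, lists "longitudinal strain and strain rate, global and segmental strain and strain rate" among the measurements to be completed in the efficacy evaluable population. Section 9.3 names no strain measure.

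**The concern.** An endpoint needs images that can show it and a stated calculation. Longitudinal strain has both. Circumferential strain has neither. Apical views cut the ventricle along its long axis, whereas circumferential shortening lies in the short-axis plane, so the loops that section 7.1 requires do not supply it.

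A site can follow section 7.1 to the letter and store nothing suited to half of the listed endpoint. Because the endpoint is a change from baseline, the gap matters most at screening: a baseline loop that was not taken, or was taken at an unsuitable level or frame rate, cannot be obtained after the infusion. If incidental clips were used instead, the plan would not control which subjects had usable data or at what LV level they were measured.

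**Working it through.** The plan gives no figure to reproduce. The check sets the endpoint beside every place where a method could appear.

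| Place | Longitudinal | Circumferential |
|---|---|---|
| Synopsis and section 4.2, exploratory endpoints | Listed | Listed |
| Section 7.1, Echocardiography: speckle-tracking views | Three apical views | No short-axis view named |
| Section 7.1, Echocardiography: offline analysis | Segmental and global | None |
| Sections 7.2.1, 7.3 (Day 90), 7.4 and Appendix A | Speckle tracking required, no views given | Same |
| Section 7.1, Cardiac MRI | No strain output | No strain output |
| Section 4.1, core laboratory | Assigned to MRI only | Assigned to MRI only |
| Synopsis, Statistical Methods | Named | Not named; wording ambiguous |
| Section 9.3 | Not listed | Not listed |

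**Segment count.** The 18 segments could in principle hide a short-axis contribution. With three apical views and an equal split (an assumption), 18 / 3 = 6 segments per view. The apical longitudinal analysis accounts for the whole count, so nothing in it implies a further view.

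**Components with a method.** The endpoint names two directions of strain. Longitudinal has an acquisition and a calculation; circumferential has neither. That is 1 of 2 directions. Counting strain and strain rate separately, it is 2 of 4 quantities, although the plan lists them as a single item.

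**Visits concerned.** Echocardiography is scheduled at screening, Day 90 and Day 180, with a further study at early termination. The gap is the same at each.

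**The case against.** The strongest reply is that a gap in the specification does not mean a gap in the data. Every scheduled echo is a full 2D and Doppler study, and section 7.1 names the three apical views without forbidding others. Short-axis clips may well be recorded, and some might be trackable. This stands. A reader might infer that the circumferential measures will have no data or cannot be reported; the documents do not support that. They support only that nothing requires suitable loops, fixes their level or frame rate, or tells anyone to analyse them.

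The synopsis wording is also a fair objection. In "longitudinal strain and strain rate, global and segmental strain and strain rate" the second phrase is not limited to longitudinal strain and could be read to cover circumferential measures. It is therefore no proof of an omission. It is no method either.

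It would be tempting to size the gap as 3 echoes x 20 subjects = 60 lost studies. That overstates it. Those echoes still yield the volumes, ejection fraction, longitudinal strain, pulmonary pressure and mitral regurgitation severity. Nor is 20 a fixed total: sections 4.1 and 5.1 call it a minimum, and section 5.3 allows replacements.

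Finally, the endpoint is exploratory, section 9 calls the analyses descriptive, and section 9.4 states that the sample size does not rest on power. No safety, eligibility or stopping decision uses circumferential strain. This too stands, and it limits the weight of the point.

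**Conclusion.** The concern holds as an inconsistency between the endpoint lists and the methods: circumferential strain and strain rate are listed twice, and the protocol specifies no acquisition or calculation for them. Whether any usable data arise is left to what each site happens to record.

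The size is minor. One component of one exploratory endpoint is affected; the primary safety endpoint, the secondary LVEF endpoint and longitudinal strain are untouched. It still deserves correction, because unsuitable baseline loops cannot be replaced later and the remedy is small.

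The conclusion rests on two assumptions. The first is the imaging geometry, which the documents do not spell out: circumferential strain needs short-axis planes. The second is that no separate imaging instruction adds such views; none is mentioned in the documents.

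**What to change.** Settle one of two options before the first screening echo.

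1. **Keep the measure.** In section 7.1, Echocardiography, add high frame-rate parasternal short-axis loops at stated LV levels at screening, Day 90 and Day 180. Add circumferential strain and strain rate to the offline analysis, and name them in the synopsis under Statistical Methods so that the wording there is no longer ambiguous. The cost is a few extra loops in an echo already scheduled and some added reading time. Section 7.1 names its workstation software only for longitudinal output, so confirm that it also gives the circumferential one.
2. **Drop the measure.** Delete the circumferential component from the exploratory endpoints in the synopsis and in section 4.2. The cost is the loss of one exploratory measure.

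Either option makes the endpoint and its method agree.
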